[figure not shown]

Efficacy of Intercostal CryoAnalgesia in Patients Undergoing Robot Assisted Anatomic Lung Resection

PROTOCOL SUMMARY

Synopsis

Title:	Efficacy of Intercostal CryoAnalgesia in Patients Undergoing Robot Assisted Anatomic Lung Resection
Short Title:	CryoNB in Robotic Lung Resection
Study Design:	Prospective randomized study
Study Objectives:	
The objectives are to determine if the addition of Cryo Nerve Block at the time of robot assisted thoracoscopic lung resection surgery will:
 
 Allow for improved postoperative analgesia as measured using Visual Analogue Scale (VAS) pain scores Allow for decreased post-operative pain medication (opioid) use Allow for accelerated recovery as measured by patient reported M.D. Anderson Symptom Inventory (MDASI) Questionnaire Increases the risk for development of neurogenic pain as measured by the Leeds Assessment of Neuropathic Symptoms and Signs (LANSS) pain scale
Number of Subjects:	40 (20 in each group)
Sites:	Single site – Froedtert Hospital/Medical College of Wisconsin Single surgeon – [name]
Study Population:	Patients undergoing robot assisted thoracoscopic anatomic lung resection (pneumonectomy, bilobectomy, lobectomy or segmentectomy)
Inclusion Criteria:	
 Age 18 - 85 years male or female Acceptable surgical candidate Willing and able to return for scheduled follow-up visits
Exclusion Criteria:	
 Patients undergoing or requiring conversion to thoracotomy Patients with chronic pain syndromes requiring treatment within the last year Patients with a history of illicit drug use Patients with a history of heavy alcohol use in the last five years as determined by the principal investigator Patients currently using opioids
Participant Duration:	Six months
Study Endpoints:	
Primary endpoints
 
 Visual Analogue Scale (VAS) Pain score on post-operative days 1-14, Day 30, Day 60, Day 90, Day 120, Day 150, Day 180 (or until a score of 0). Pain medication use daily for 21 days post-operatively 
Secondary endpoints
 
 M.D. Anderson Symptom Inventory Questionnaire on post-operative Day 1, Day 7, Day 14, Day 21, Day 30, Day 35, and Day 42 Leeds Assessment of Neuropathic Symptoms and Signs (LANSS) score at Post-Operative Day 30, Day 90, and Day 180

Schema

HYPOTHESIS

The addition of Cryo Nerve Block to a standard postoperative pain regimen will improve analgesia and facilitate recovery following robot assisted thoracoscopic anatomic lung resection

SPECIFIC AIMS

This study will determine if the addition of Cryo Nerve Block during robot assisted thoracoscopic anatomic lung resection surgery will:

PRIMARY ENDPOINTS:

- Allow for improved postoperative analgesia as measured using Visual Analogue Scale (VAS) pain scores
- Allow for decreased post-operative pain medication (opioid) usage

SECONDARY ENDPOINTS:

- Allow for accelerated recovery as measured by patient reported M.D. Anderson Symptom Inventory (MDASI) Questionnaire
- Increases the risk for development of neurogenic pain as measured by the Leeds Assessment of Neuropathic Symptoms and Signs (LANSS) pain scale

RATIONALE FOR THE PROJECT

Thoracic surgical procedures are consistently reported to be among the most painful surgical incisions currently used.¹ Trauma to the skin, muscle, intercostal nerves, bones and pleura all contribute and lead to activation of various pain pathways including somatic, visceral, neurogenic and phrenic.¹ In the short term, this pain leads to ineffective cough and pulmonary hygiene resulting in respiratory complications and prolonged hospital stays while in the longer term it leads to prolonged recovery, delayed return to work and in some instances, chronic post thoracotomy pain syndromes.² Minimally invasive approaches such as standard thoracoscopy or robotic assisted thoracoscopy have certainly decreased some of this trauma as evidenced by decreased length of stays and decreased complication rates however even with these minimally invasive techniques, recovery to 80% of baseline is 25 days³ and 9.4% of patients are still using narcotics after 90-180 days.⁴

Several options are available in the management of pain following thoracic surgery with a multimodal pain medicine approach being most common. Opioids, unfortunately, are a relatively large part of this approach and are often relied upon despite their relatively unfavorable adverse event profile and risk for addiction. Many of the other pain adjuncts often used with thoracotomies such as epidural catheters or intraoperatively placed pain catheters are not really reasonable when using minimally invasive approaches as the hospital length of stay is 1-2 days. Intercostal cryoanalgesia has been shown to be a safe and effective strategy for post-operative pain management in patients undergoing thoracotomy.^{5,6} Recent studies have demonstrated the beneficial effect of cryoanalgesia for post-thoracotomy pain in reduction of opioid requirement, reduction in post-operative pain scores, and superior pulmonary function (higher FEV1 and FVC values)⁵ and that it can produce temporary neurolysis for up to two months without long-term histological nerve damage.⁶ To date it has not been studied when using minimally invasive techniques whether it be standard thoracoscopy or robotic assisted thoracoscopy but it would stand to reason that it would be equally or maybe more effective in this patient population and truly maximize the benefits of a minimally invasive approach .

We therefore propose to assess whether intra-operative intercostal cryoanalgesia using the cryoICE® probe provides superior post-operative analgesia as compared to our current standard pain management strategy in patients undergoing robotic assisted thoracoscopic anatomic lung resection and allows for decreased opioid use and more rapid recovery.

PROJECT DESIGN AND PROTOCOL

DESIGN

This is a single center, single surgeon, prospective, randomized trial examining the addition of Cryo Nerve Block during robot assisted thoracoscopic anatomic lung resection surgery

SUBJECTS IN THE STUDY

40 total subjects will be enrolled in the study – 20 in each group

Inclusion Criteria

- Patients undergoing robot assisted thoracoscopic anatomic lung resection surgery
- Male or female age 18 or older
- Acceptable surgical candidate
- Willing and able to return for scheduled follow-up visits

Exclusion Criteria

- Patients undergoing or requiring conversion to thoracotomy
- Patients with chronic pain syndromes requiring treatment in the last year
- Patients with a history of illicit drug use
- Patients with a history of heavy alcohol use in the last five years as determined by the principal investigator
- Patients currently using opioids

CONSENT

All patients eligible for this study will be approached for consent to enter the study in compliance with Human Research Review Committee (HRRC) standards. Consent will be obtained by the principal investigator or authorized delegate.

RANDOMIZATION PROCESS

Following the attainment of consent to enter the study, patients will be randomized to either the standard postoperative pain regimen or the standard postoperative pain regimen plus cryo nerve block by a blinded procedure where a card indicating either group will be drawn in a witnessed setting by a noninvestigator.

PROCEDURE

All patients will be assessed at baseline and then taken to the operating room for robot assisted thoracoscopic anatomic lung resection surgery. Each operation will be performed by the same surgeon and port placement will be identical (aside from laterality) in each patient. All patients will have the first two ports placed at which time an intercostal nerve block of nerves 4-9 will be performed using 0.5% Marcaine with Epinephrine. Additionally, in the study group, Cryo Nerve Block of nerves 4-9 will also be performed. To perform the cryo nerve block the 18 inch Atricure® cryoSPHERE Probe will be used in each case. The remaining ports will then be placed, the robot docked, and the procedure performed. Following the procedure, a chest tube will be placed through the camera port. Postoperatively, all patients will receive the standard post-operative pain regimen currently used by the Thoracic Surgery Service at Froedtert Hospital/Medical College of Wisconsin which consists of Tylenol and Robaxin around the clock and Ultram as first line analgesia for breakthrough pain and Oxycodone as the second line agent if necessary.

RISKS AND PRECAUTIONS

The pain management strategy outlined above, whether with or without cryo nerve block, is the current standard pain management strategy following robot assisted thoracoscopic lung

resection surgery at Froedtert Hospital/Medical College of Wisconsin. Both are routinely employed and it must be stressed that neither arm is experimental in any way with both modalities currently in use and being used successfully. What is unclear at present is which approach offers greater advantage to the patient in terms of improved analgesia and facilitation of recovery.

Risks inherent to this study are those associated with the operative procedure of robot assisted thoracoscopic lung resection surgery. To date there have been no reports of acute adverse events with cryo nerve block.

DATA COLLECTED

As shown in the schema, the following data will be collected

Preoperatively – within 30 days of surgery

- Characteristics (Age, gender, race, marital status, ECOG function, height, weight, BMI, tobacco use, major comorbidities)
- Baseline VAS Score
- Baseline MDASI
- Baseline LANSS

Intraoperatively – at time of surgery

- Procedure
- Procedure duration
- Port placement
- Intraoperative complications
- Estimated blood loss (EBL)

Postoperatively – at designated time points

- Length of stay
- Chest tube duration
- Complications
- VAS pain scores daily on post-operative Days 1-14, Day 30, Day 60, Day 90, Day 120, Day 150, Day 180 (or until score of 0).
- Pain med usage daily for post-operative Days 1-21
- MDASI questionnaire on post-operative Day 1, Day 7, Day 14, Day 21, Day 30, Day 35, and Day 42
- LANSS score at Day 30, Day 90 and Day 180

A time frame of data collection points is shown below and the VAS scale, MDASI Questionnaire, and LANSS pain scale are included in the appendix.

Day	Characteristics	VAS	MDASI	LANSS	Pain meds
Baseline	X	X	X	X	X
0					
1		X	X		X
2		X			X
3		X			X
4		X			X

5		X			X
6		X			X
7		X	X		X
8		X			X
9		X			X
10		X			X
11		X			X
12		X			X
13		X			X
14		X	X		X
15					X
16					X
17					X
18					X
19					X
20					X
21			X		X
22					X
30 (+/- 2 days)		X	X	X	
35 (+/- 2 days)			X		
42 (+/- 2 days)			X		
60 (+/- 5 days)		X			
90 (+/- 5 days)		X		X	
120 (+/- 5 days)		X			
150 (+/- 5 days)		X			
180 (+/- 5 days)		X		X	

REFERENCES

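### The primary VAS series may stop at a patient's first score of 0, so follow-up depends on the primary outcome and pain that returns after a temporary block goes unrecorded

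*Protocol*

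**What the plan says.** The Synopsis (Study Endpoints) lists VAS pain as a primary endpoint on "post-operative days 1-14, Day 30, Day 60, Day 90, Day 120, Day 150, Day 180 (or until a score of 0"). Data Collected repeats the schedule and ends in the same way: "Day 150, Day 180 (or until score of 0"). Neither place says which visits the clause governs, or how visits after a 0 are to be treated.

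The schedule table in Data Collected marks VAS on each of Days 1 to 14 and at all six later visits, with no condition attached.

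The Rationale says of the intervention that "it can produce temporary neurolysis for up to two months", and gives as an aim that the block "allows for decreased opioid use and more rapid recovery".

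The other primary endpoint is "Pain medication use daily for 21 days post-operatively". The matching aim reads "Allow for decreased post-operative pain medication (opioid) usage". Data Collected has "Pain med usage daily for post-operative Days 1-21", while the table also marks pain medication on Day 22.

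**The concern.** A rule that ends measurement when the outcome reaches a given value makes the amount of data depend on the outcome. If the block works, more patients in that arm should reach 0, and reach it sooner, so the arms could differ in how much follow-up they contribute.

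Two things are at stake.

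- **Returning pain.** The block is expected to wear off. A patient who scores 0 while it is active and has pain again later would leave no VAS record of that pain, so the late part of the primary series would be least complete where it is most needed.
- **Faster recovery.** This is part of the hypothesis. It can vanish from a summary of recorded scores, because a patient who recovers sooner contributes fewer low values.

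An analysis plan can choose how to handle missing scores. It cannot supply scores that the protocol told staff not to collect.

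**Working it through.** **Inputs.** The VAS days come from the Synopsis and the Data Collected table. The duration of neurolysis comes from the Rationale. The falling score patterns below are illustrations and do not come from the protocol.

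**Scheduled times.** 14 daily scores + 6 later visits (Days 30, 60, 90, 120, 150, 180) = 20.

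**Scores lost under each reading of the clause.**

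| Reading | First 0 | Recorded | Lost of 20 |
|---|---|---|---|
| Ends the series at any time | Day 5 | 5 | 15 (75%) |
| Ends the series at any time | Day 10 | 10 | 10 (50%) |
| Days 1-14 kept, but an early 0 cancels later visits | Day 10 | 14 | 6 (30%) |
| Applies to later visits only | Day 30 | 14 + 1 = 15 | 5 (25%) |
| Applies to later visits only | Day 60 | 14 + 2 = 16 | 4 (20%) |

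The first reading contradicts the table, which marks VAS on all of Days 1-14. The others are compatible with the daily marks to Day 14, but every one of them loses later visits. In the last row the four lost visits (Days 90, 120, 150, 180) all fall after the cited two months, which is when returning pain would appear.

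**What averaging recorded scores does, on the literal reading.** Let a patient's score fall evenly from 4 on Day 1 to 0 on Day k and stay at 0.

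- Sum of scores = k × (4 + 0)/2 = 2k.
- Mean of recorded scores, including the final 0 = 2k/k = 2.0 for every k.
- Mean over Days 1-14 with the remaining days at 0 = 2k/14.

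For k = 5 the sum is 10, giving 10/5 = 2.0 as recorded and 10/14 = 0.71 over 14 days. For k = 10 the sum is 20, giving 20/10 = 2.0 as recorded and 20/14 = 1.43 over 14 days.

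Recovery in half the time shows no difference on recorded scores, against 1.43 − 0.71 = 0.71 points (10/14 before rounding) on the full 14 days.

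**Whether filling in zeros repairs it.** Setting every score after the first 0 to 0 restores the 0.71 and 1.43, but only because the illustration assumes that pain stays at 0. For the later visits that assumption sits badly with a block described as temporary, and the data needed to check it would not exist.

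**Whether another instrument fills the gap.** MDASI item 1 (Appendix III) rates worst pain from 0 to 10, but its last administration is Day 42. LANSS is collected at Days 30, 90 and 180, but the version in Appendix IV scores neuropathic features, not pain intensity. Neither replaces VAS from Day 60 onward.

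**Medication wording.** The endpoint line says pain medication, while the objectives and aims add opioid in parentheses. Under Procedure, all patients receive two non-opioid agents around the clock, with "Ultram as first line analgesia for breakthrough pain and Oxycodone as the second line agent if necessary". The two wordings therefore describe different variables. The text stops at Day 21 and the table at Day 22.

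**The case against.** The strongest reply is that the literal reading is not the natural one. The clause follows Day 180 in both places, Data Collected calls for daily scores on Days 1-14, and the table marks each of those days. Together these favour full collection to Day 14, with the clause shortening later follow-up only. That is fair, and a reader should not infer that early scores will certainly be lost. But the text does not say so, and the later-visit reading still leaves returning pain unrecorded.

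A second reply is that the 2.0 against 2.0 example is built to tie. It is: any even fall to 0 averages half its starting value. It shows what can happen and does not forecast the trial. It already counts the 0 that triggered stopping, so the tie does not come from discarding that score. An analyst who filled later days with 0 would avoid it, at the price of assuming that pain never returns.

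A reader might also infer that the primary endpoints are undefined, because the protocol names no per-patient summary, primary window, ranking or multiplicity method. The document does not support that as an error. Such choices may sit in a statistical analysis plan that is not shown, and they are not part of this point.

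On medication, the reply is that the objectives and aims already say opioid, so the endpoint line is shorthand, and that Day 22 is clerical. Both are largely right, which is why these items are minor.

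**Conclusion.** The point holds as a defect in a stated collection rule. On any reading, the clause allows a primary-outcome value to end later primary-outcome collection. In the cases worked above, the loss runs from 4 to 15 of 20 scheduled scores for a patient who reaches 0, depending on when that happens and how the clause is read.

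The documents do not give the proportion of patients who will reach 0, how that will differ by arm, or how often pain returns. The net bias in the treatment comparison therefore cannot be sized, and its direction is not established. The difference in missing data between arms is a possibility that follows from the rule, not a demonstrated effect. The concern about returning pain rests on the protocol's own description of the block as temporary. The masking of faster recovery rests on the literal reading and on a summary that uses recorded scores only.

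The two medication mismatches are real but minor, and would not justify a comment of this weight on their own.

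**What to change.** Delete the stop clause from the Synopsis and from Data Collected. State that VAS is collected at every scheduled time through Day 180, whatever the earlier scores. If time to first 0 is of interest, derive it from the complete series. Limiting the clause to visits after Day 14 would not be enough, because returning pain would still be missed.

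In the same edit, make the medication endpoint line match the opioid wording of the objectives and aims, and reconcile Day 21 in the text with Day 22 in the table.

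The cost is some extra 0-10 ratings from patients who have already scored 0. Up to Day 14 these fall on days when medication use is recorded anyway, and at Days 30, 90 and 180 they coincide with LANSS. At Days 60, 120 and 150 VAS is the only item in the table, so for these patients those contacts are the real added burden. They lie within the stated six-month participation and are already on the schedule. The sample size and the other assessments are unaffected.

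### Conversion to thoracotomy is listed as an exclusion criterion, but it can be known only after randomisation and normally after the block, so the rule leads to post-randomisation exclusion

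*Protocol*

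**What the plan says.** The Synopsis and the Exclusion Criteria under SUBJECTS IN THE STUDY carry the same entry: "Patients undergoing or requiring conversion to thoracotomy". As the wording is identical in both places, it is not a slip in one list.

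The order of events is set out in three later sections of the protocol:

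- CONSENT: "All patients eligible for this study will be approached for consent to enter the study". Eligibility is therefore judged before consent.
- RANDOMIZATION PROCESS: "Following the attainment of consent to enter the study, patients will be randomized". Allocation is by a card drawn after consent.
- PROCEDURE: "All patients will have the first two ports placed at which time an intercostal nerve block of nerves 4-9 will be performed", with the cryo block added at this step in the study group. After that, "The remaining ports will then be placed, the robot docked, and the procedure performed".

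PROCEDURE also states "Each operation will be performed by the same surgeon". The visible text does not say whether a converted patient stays in follow-up, is replaced, or is analysed.

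**The concern.** An eligibility criterion has to be decidable when eligibility is assessed. Conversion is an intraoperative event, so listing it as an exclusion makes it a rule for removing patients after allocation.

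Two features make this more than a matter of wording. First, converted patients plausibly differ on both primary endpoints, pain score and pain medication use. RATIONALE FOR THE PROJECT mentions, as general background, "Many of the other pain adjuncts often used with thoracotomies such as epidural catheters or intraoperatively placed pain catheters", so pain and opioid use after a conversion may partly reflect different analgesia. Second, one surgeon performs every operation and cannot be unaware of whether cryo was given, so the event that triggers exclusion normally arises with the allocation known.

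At stake is whether the groups compared are still the groups that were randomised. Site staff who read the entry literally could also stop collecting pain scores, medication records and questionnaires from converted patients, and a later analysis plan could not recover those data.

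**Working it through.** **Sequence check.** There is no figure in the protocol to reproduce: it gives 40 patients, 20 per group, but no conversion rate, SD, target difference, alpha or power. The main check is therefore the order of events.

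| Step | Protocol section | Can conversion be known? |
|---|---|---|
| Eligibility and consent | CONSENT | No |
| Card drawn | RANDOMIZATION PROCESS | No |
| First two ports, local anaesthetic block, cryo in study group | PROCEDURE | Only if the need appears at port placement |
| Remaining ports, docking, resection | PROCEDURE | Yes, normally here |

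The exact moment of the card draw is not given, but it follows consent and must precede the block. The conversion part of the criterion can thus act only after randomisation, and normally after the block.

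**How often the rule would be triggered.** The conversion rate p is an assumption, shown over a range.

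- Expected conversions = 40p.
- Chance of at least one = 1 − (1 − p)^40.
- Chance of unequal numbers by arm, with no effect of arm: two independent Binomial(20, p) counts differ.

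| p | Expected of 40 | At least one | Arms unequal | Arms differ by 2 or more |
|---|---|---|---|---|
| 2% | 0.8 | 1 − 0.98^40 = 0.554 | 0.477 | 0.084 |
| 5% | 2 | 1 − 0.95^40 = 0.871 | 0.690 | 0.253 |
| 10% | 4 | 1 − 0.90^40 = 0.985 | 0.786 | 0.417 |

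The last two columns show chance imbalance, not bias.

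**What one or two exclusions can do to a mean (illustration).** Assume that converted patients score 3 points higher and that the SD is 2.

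- Excluding one patient from an arm of 20 moves that arm's mean by 3/20 = 0.15; excluding two moves it by 6/20 = 0.30.
- Standard error of the difference = 2 × √(2/20) = 0.632.
- The shifts are 0.15/0.632 = 0.24 and 0.30/0.632 = 0.47 standard errors, if the exclusions all fall in one arm.

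**Cost of keeping converted patients.** Two-sample t test, two-sided alpha 0.05, 80% power (all assumed). Keeping them raises the SD to √(4 + p(1 − p) × 9). Dropping them leaves the SD at 2 but reduces the number per arm to 20(1 − p).

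| p | Kept: 0.909 × SD | Dropped: d × 2 (n per arm) |
|---|---|---|
| 2% | 0.909 × 2.04 = 1.86 | 0.919 × 2 = 1.84 (19.6) |
| 5% | 0.909 × 2.10 = 1.91 | 0.934 × 2 = 1.87 (19) |
| 10% | 0.909 × 2.19 = 1.99 | 0.961 × 2 = 1.92 (18) |

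The largest loss is 1.99 − 1.92 = 0.07 points.

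**The case against.** The strongest reply is that the harmful step is inferred. The protocol never says that converted patients are dropped from the analysis, and the analysis population is commonly left to a SAP, which is not shown. The schema figure is also missing and might show how conversions are handled. All of that is true. It does not rescue the criterion, because an eligibility rule belongs to the protocol and no figure can make an intraoperative event knowable at screening. A SAP that kept everyone would conflict with the exclusion list; a SAP that followed the list would drop patients after allocation.

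A second reply is that no route to bias is shown. If the arm does not affect conversion and exclusion is automatic, dropping converted patients leaves a fair comparison among operations completed robotically, which is close to the population in the title. This stands as a limit on the claim: bias is possible, not demonstrated. It also supports reporting that analysis, but as a secondary view, because the trial cannot verify the condition on which it depends.

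Third, the remark on epidural and pain catheters is background, and PROCEDURE prescribes the same standard regimen for all patients. Different analgesia after conversion is therefore only plausible. Likewise, the shifts of 0.24 and 0.47 standard errors apply only when the exclusions fall in one arm. Both points stand, and the conclusion depends on neither.

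**Conclusion.** The concern holds. The conversion part of the criterion cannot be applied when eligibility is assessed. Followed as written, it removes patients after randomisation and normally after the block. The sequence follows directly from the protocol text and rests on no assumption.

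The consequence is less certain. Over an assumed conversion rate of 2% to 10%, at least one such patient among 40 is more likely than not (0.55 to 0.985), and with 20 per arm even one or two exclusions are noticeable. The size and direction of any bias are unknown, because nothing in the protocol shows that the arm affects conversion or the decision to exclude. This should be fixed before enrolment: the flaw is clear and the correction is small.

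**What to change.** 1. In both eligibility lists, limit the criterion to what is known before randomisation: thoracotomy planned before the card is drawn.
2. State that every randomised patient is followed on the full schedule and analysed in the assigned group in the primary analysis, whether or not the operation was converted. Report conversions by arm, and give the analysis without converted patients as a sensitivity analysis.
3. Optional: draw the card in the operating room once the robotic approach is confirmed. This avoids only early conversions and does not replace item 2.

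Items 1 and 2 cost a wording change in two lists and a short statement on follow-up and analysis. The statistical price is slightly more outcome variance, at most about 0.07 points of detectable difference at an assumed 10% conversion rate, SD of 2 and 3-point gap. Item 3 needs a noninvestigator and a witness in the operating room.

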APPENDIX II – Visual Analogue Scale Pain Score

UNIVERSAL PAIN ASSESSMENT TOOL

This pain assessment tool is intended to help patient care providers assess pain according to individual patient needs. Explain and use 0-10 Scale for patient self-assessment. Use the faces or behavioral observations to interpret expressed pain when patient cannot communicate his/her pain intensity.

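### The card draw is tied only to consent and no text shown keeps the arm from the patient, who rates or drives both primary endpoints; a later draw and a non-disclosure rule would be a cheap improvement

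*Protocol*

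**What the plan says.** **Allocation.** Protocol, RANDOMIZATION PROCESS: "Following the attainment of consent to enter the study, patients will be randomized" to standard pain management with or without cryo nerve block, "by a blinded procedure where a card indicating either group will be drawn in a witnessed setting by a noninvestigator". The section sets no latest time for the draw and does not require baseline to be complete.

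**Baseline.** PROCEDURE: "All patients will be assessed at baseline and then taken to the operating room". DATA COLLECTED places the baseline VAS, MDASI and LANSS under "Preoperatively – within 30 days of surgery".

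**What differs between arms.** PROCEDURE states that "port placement will be identical (aside from laterality) in each patient" and that every patient receives the Marcaine intercostal block. Cryo is an additional operating-room step in one arm.

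**Primary endpoints.** These are VAS pain and pain medication (opioid) use. Appendix II makes the scale a patient self-assessment and allows a fallback: "Use the faces or behavioral observations to interpret expressed pain when patient cannot communicate his/her pain intensity". Opioid use comes from Ultram, then Oxycodone, for breakthrough pain on top of scheduled medicines.

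**Hypothesis.** It is directional: cryo "will improve analgesia and facilitate recovery following robot assisted thoracoscopic anatomic lung resection".

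The synopsis and DESIGN call the trial prospective and randomized. Neither labels it blinded or open-label.

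**The concern.** A reader who meets the word 'blinded' in the randomization section may take the trial to be masked. The wording supports only a concealed draw. Concealment protects against choosing which patient goes to which arm. It does nothing about what the patient knows afterwards.

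That matters here because both primary endpoints pass through the patient. Someone who knows that they received the added block, in a study expecting it to relieve pain, could score pain lower and ask for or take less breakthrough opioid. Both shifts favour the hypothesis. They would look exactly like a treatment effect, so no later analysis could separate the two.

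A smaller point concerns order. If the draw comes before baseline and the patient learns the arm, the baseline self-reports are open to the same influence.

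**Working it through.** **1. What the text fixes about masking.**

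| Question | Text shown |
|---|---|
| What is 'blinded'? | The card draw only |
| Is the patient kept unaware of the arm? | Not stated |
| Is the patient told the arm? | Not stated |
| Is the trial called open-label? | No |
| When is the draw? | After consent, no other condition |
| When is baseline? | Before the operating room, up to 30 days before surgery |
| Is baseline before the draw? | Not stated |

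The draw and the baseline are each placed relative to something else (consent and surgery), never relative to each other. Both orders comply with the text.

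**2. How much primary data the patient generates alone.** Inputs: the schedule in DATA COLLECTED and the 1-2 day stay in RATIONALE FOR THE PROJECT. That stay is a general remark about minimally invasive surgery, not a trial rule.

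- Post-operative VAS points: Days 1-14 (14) plus Days 30, 60, 90, 120, 150 and 180 (6) = 20.
- Discharge on Day 1: 14 − 1 = 13 daily VAS, 20 − 1 = 19 of all VAS points, and 21 − 1 = 20 medication days fall after discharge.
- Discharge on Day 2: 14 − 2 = 12, 20 − 2 = 18 and 21 − 2 = 19.

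The VAS counts are maxima. Collection carries the note "Day 150, Day 180 (or until score of 0", which may let a reported 0 end collection, although its scope is unclear and the schedule table shows no such stop. After discharge, what the patient knows matters more than what ward staff know.

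**3. Can the patient be masked without a sham?** Ports and the Marcaine block are common to both arms, and the cryo step takes place in the operating room. A patient already anaesthetised when the card is drawn has not been told the arm and does not witness the step.

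**4. How far can later sensation unmask?** RATIONALE FOR THE PROJECT gives temporary neurolysis of up to two months. That window covers:

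- VAS Days 1-14 and 30: 14 + 1 = 15 of 20 points, or 16 if Day 60 counts
- all 21 medication days
- all 7 post-operative MDASI forms
- 1 of 3 post-operative LANSS assessments (Day 30)

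MDASI item 13 and S-LANSS item 7 both ask about numbness. Some cryo patients may therefore infer their arm.

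**5. Illustration only: what a reporting shift would do.** Assume one VAS comparison by two-sample t-test, 20 per arm, two-sided 5%, no true effect, and a reporting shift of b standard deviations (SD). The degrees of freedom are 20 + 20 − 2 = 38, the critical value is 2.024, and the noncentrality is b / √(2/20) = b / 0.316.

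| Shift b (SD) | Noncentrality | Rejection rate |
|---|---|---|
| 0 | 0 | 5.0% |
| 0.1 | 0.316 | 6.1% |
| 0.21 | 0.669 | 10% |
| 0.25 | 0.791 | 12.0% |
| 0.5 | 1.581 | 33.8% |

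The 10% row was solved for and holds at b = 0.2116. The Protocol text shown gives no shift, SD or significance level, and medication use is not modelled. The conclusion does not rest on this table.

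**The case against.** **Open-label is legitimate, and the text makes no false claim.** This stands. 'Blinded' is attached to the draw, and the Protocol never calls the trial masked. A reader might infer that the Protocol claims to be blinded and is not, or that patients are told their arm. Neither is supported: knowledge of the arm is left open, not prescribed. What remains is that a better procedure is available at low cost.

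**The schema or consent pages may settle it.** This is possible. The Protocol refers to a schema, whose figure is not shown, and consent wording may say what patients learn. If either fixes the order or the disclosure, the change reduces to bringing RANDOMIZATION PROCESS into line with it. The statistical analysis plan, also not shown, does not answer the point, because it cannot mask patients.

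**The order of draw and baseline has little consequence.** This largely stands. The primary endpoints are post-operative, and no primary measure of change from baseline is stated. A reader might infer that a shifted baseline distorts the primary result; the Protocol shows no route for that. The order is secondary and is corrected by the same edit.

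**Numbness will unmask patients anyway.** This stands in part. Masking will be incomplete, and how much bias it removes cannot be quantified. Even so, inference by some patients is weaker than leaving every patient free to be told.

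**The error rates are alarming and assumed.** Agreed. A reader might take them as the trial's false-positive rate, which they are not.

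**The observer fallback calls for a masked collector.** It applies only when a patient cannot communicate, so it adds little.

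**Conclusion.** The point holds as a worthwhile, inexpensive improvement, not as an error or contradiction in the Protocol. On the text shown, the draw is tied only to consent and nothing keeps the arm from the patient, so both primary endpoints are open to expectation bias in the direction of the hypothesis.

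The size of that bias is unknown. What can be stated is the exposure: 18-19 of 20 post-operative VAS points and 19-20 of 21 medication days after discharge, assuming that the general stay applies to these patients.

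The conclusion rests on two assumptions: that the unseen schema and consent pages do not already settle order and disclosure, and that a useful share of patients would not work out their arm from numbness. Confidence is medium. The change should be made, but the trial is not invalid without it.

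**What to change.** In RANDOMIZATION PROCESS:

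1. Require the baseline VAS, MDASI and LANSS to be complete before the card is drawn.
2. Keep the noninvestigator and the witness, but draw the card in the operating room once the patient is anaesthetised.
3. State that the patient is not told the arm until Day 180 unless it is needed for care.
4. Align the consent wording and the schema, and state in the report that masking was partial because numbness may reveal the arm.

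No restriction on charting the procedure or on what treating staff know is requested. Where existing staffing allows, follow-up scores can be collected by someone not told the arm; this is optional. Asking patients to guess their arm is not recommended, because a guess would be confounded with real pain relief. If the sponsor prefers not to mask the patient, DESIGN should call the trial open-label, and baseline should still come before the draw.

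**Cost.** Protocol and consent wording change, and the noninvestigator, the witness and a probe must be available for each of the 40 cases. No sham, extra visit or additional patient is needed.
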